6.4.4 Clinical Laboratory Tests

Clinical laboratory tests will be performed by PPD's central laboratory. Blood and urine samples will be collected under fasted conditions and at the time points indicated in the schedule of events ([Table 2](#)).

For women of childbearing potential only: Serum pregnancy tests will be performed at Screening. To confirm pregnancy, urine pregnancy test will be performed locally. For post-menopausal female subjects only, FSH testing will be performed at Screening.

The following hematology, coagulation, serum chemistry, and urinalysis assessments will be performed:

- Hematology: Hematocrit, hemoglobin, mean corpuscular hemoglobin, mean corpuscular hemoglobin concentration, mean corpuscular volume, platelet count, red blood cell count, total and differential (absolute and percent) leukocyte count, and erythrocyte sedimentation rate
- Coagulation: International normalized ratio, partial thromboplastin time, and prothrombin time, ABO and Rh Blood Type
- Serum Chemistry: Alanine aminotransferase, albumin, alkaline phosphatase, AST, bilirubin (total and direct if clinically indicated), blood urea nitrogen, calcium, creatinine, gamma-glutamyltransferase, glucose, lactate dehydrogenase, serum electrolytes (sodium, potassium, chlorine, magnesium, phosphate) and total protein
- Urinalysis: Appearance, bilirubin, color, glucose, ketones, leukocyte esterase, microscopy (performed if dipstick is positive; includes bacteria, casts, crystals, epithelial cells, red blood cells, and white blood cells), nitrites, occult blood, pH, protein, specific gravity, turbidity, and urobilinogen

Abnormal clinical laboratory values will be flagged as either high or low (or normal or abnormal) based on the reference ranges for each laboratory parameter. The investigator will determine whether any abnormally high or low results are clinically significant or not clinically significant. Clinical significance is defined as any variation in results that has medical relevance and may result in an alteration in medical care (eg, active observation, diagnostic measures, or therapeutic measures). If a clinically significant change from the screening value is noted, the clinically significant value and the reason for clinical significance will be documented on the AE page of the subject's eCRF. The investigator will continue to monitor the subject with additional assessments until the values have reached either the reference range or the values at Screening or until the investigator determines that follow-up is no longer medically necessary.

The FDA guidance for industry on Drug-Induced Liver Injury: Premarketing Clinical Evaluation (July 2009) will be used as a guideline for the assessment of liver enzymes/liver function tests ([DHHS 2009](#)).

Clinically significant laboratory values for individual subjects will be listed. A summary for the numbers and percentages of subjects with clinically significant laboratory values at any time point will be presented.

6.4.5 Adverse Events

6.4.5.1 Definitions of Adverse Events

The investigator is responsible for reporting all TEAEs that are observed or reported during the study, regardless of their relationship to study drug or their clinical significance.

An AE is defined as any untoward medical occurrence in a subject enrolled into this study regardless of its causal relationship to study drug. Subjects will be instructed to contact the investigator at any time after randomization if any symptoms develop.

A TEAE is defined as any event not present before exposure to study drug or any event already present that worsens in either intensity or frequency after exposure to study drug.

6.4.5.2 Serious Adverse Events

An SAE is defined as any event that:

- Results in death
- Is immediately life threatening
- Requires inpatient hospitalization or prolongation of existing hospitalization
- Results in persistent or significant disability/incapacity
- Is a congenital anomaly/birth defect

Important medical events that may not result in death, be life threatening, or require hospitalization may be considered SAEs when, based upon appropriate medical judgment, they may jeopardize the subject or may require medical or surgical intervention to prevent one of the outcomes listed in this definition. Examples of such medical events include allergic bronchospasm requiring intensive treatment in an emergency room or at home, blood dyscrasias or convulsions that do not result in inpatient hospitalization, or the development of drug dependency or drug abuse.

Note: The AE terms neutropenia and hypertension should be used only when reporting events that meet the following criteria:

- The term neutropenia is reserved for reporting an absolute neutrophil count $<1000/\text{mm}^3$ or $<1.0 \times 10^9/\text{L}$ and may or may not be associated with fever or concurrent infection.
- The term hypertension is reserved for reporting an increase in systolic blood pressure $\geq 160 \text{ mmHg}$, or diastolic blood pressure $\geq 100 \text{ mmHg}$, or any clinically significant increase in blood pressure that requires modification of the subject's antihypertensive regimen.

6.4.5.3 Eliciting and Documenting Adverse Events

Adverse events will be assessed from the time the subject signs the informed consent form until end of study visit (Week 16).

If the investigator becomes aware of an SAE that occurs after the end of study visit and is assessed by the investigator as at least possibly related to the study drug, they need to report the SAE.

At every study visit, subjects will be asked a standard nonleading question to explore a response regarding any medically related changes in their well-being. They will also be asked if they have been hospitalized, had any accidents, used any new medications, or changed concomitant medication regimens (both prescription and over-the-counter medications).

In addition to subject observations, AEs identified from any study data (eg, laboratory values, physical examination findings, ECG changes) or identified from review of other documents that are relevant to subject safety will be documented on the AE page in the eCRF.

6.4.5.4 Reporting Adverse Events

All AEs reported or observed during the study will be recorded on the AE page in the eCRF. Information to be collected includes drug treatment, dose, event term, time of onset, investigator-specified assessment of severity and relationship to study drug, time of resolution of the event, seriousness, any required treatment or evaluations, and outcome. Adverse events resulting from concurrent illnesses, reactions to concurrent illnesses, reactions to concurrent medications, or progression of disease states must also be reported. All AEs will be followed to adequate resolution. The Medical Dictionary for Regulatory Activities (MedDRA v20.0) will be used to code all AEs. All AEs, SAEs, drug-related AEs, and drug-related SAEs will be summarized using the worst grade per NCI CTCAE v5.0 by system organ class and preferred term.

Any medical condition that is present at the time that the subject is screened but does not deteriorate should not be reported as an AE. However, if it deteriorates at any time during the study, it should be recorded as an AE.

6.4.5.5 Reporting Serious Adverse Events

Any AE that meets SAE criteria ([Section 6.4.5.2](#)) must be reported to PPD immediately (ie, within 24 hours) after the time that site personnel first learn about the event. The nonserious adverse event of special interest (AESI) defined in [Section 6.4.5.6](#) should be recorded on the SAE report form in addition to the eCRF and faxed using the same process as for reporting SAEs.

Pharmacovigilance**6.4.5.6 Suspected Unexpected Serious Adverse Reactions and Nonserious Adverse Events of Special Interest**

The following nonserious AESI should be recorded on the SAE report form in addition to the eCRF and faxed using the same process as for reporting SAEs.

- **Neutropenia** with fever defined as absolute neutrophil count $<1000/\text{mm}^3$ or $<1.0 \times 10^9/\text{L}$ on the most recent complete blood count with fever equal to or greater than 38°C that does not fulfill any of the serious criteria, ie, hospitalization.
- **Hepatotoxicity** defined as ALT $>3 \times \text{ULN}$ plus total bilirubin $>2 \times \text{ULN}$ that does not fulfill any of the serious criteria, ie, hospitalization. This information should be recorded on the drug induced liver injury eCRF each time the elevated laboratory parameters are met during the study

Oscotec Inc. will promptly evaluate all suspected unexpected serious adverse reactions (SUSARs) and nonserious AESI against cumulative product experience to identify and expeditiously communicate possible new safety findings to investigators, Institutional Review Board (IRB)/Independent Ethics Committee (IEC), and applicable health authorities based on applicable legislation.

To determine reporting requirements for single AE cases, Oscotec Inc. will assess the expectedness of these events using the study drug investigator's brochure.

Oscotec Inc. will compare the severity of each SUSAR and the cumulative event frequency reported for the study with the severity and frequency reported in the applicable reference document.

Reporting requirements will also be based on the investigator's assessment of causality and seriousness, with allowance for upgrading by Oscotec Inc. as needed.

6.4.5.7 Assessment of Severity

The severity, or intensity, of an AE refers to the extent to which an AE affects the subject's daily activities. The intensity of the AE will be rated using the NCI CTCAE v5.0.

Changes in the severity of an AE should be documented to allow an assessment of the duration of the event at each level of intensity to be performed. Adverse events characterized as intermittent do not require documentation of the onset and duration of each episode.

6.4.5.8 Assessment of Causality

The investigator's assessment of an AE's relationship to study drug is part of the documentation process, but it is not a factor in determining what is or is not reported in the study. If there is any doubt as to whether a clinical observation is an AE, the event should be reported. The relationship or association of the study drug in causing or contributing to the AE will be characterized using the following classification and criteria:

- Unrelated: This relationship suggests that there is no association between the study drug and the reported event.
- Possible: This relationship suggests that treatment with the study drug caused or contributed to the AE, ie, the event follows a reasonable temporal sequence from the time of drug administration or follows a known response pattern to the study drug but could also have been produced by other factors.
- Probable: This relationship suggests that a reasonable temporal sequence of the event with drug administration exists and, based upon the known pharmacological action of the drug, known or previously reported adverse reactions to the drug or class of drugs, or judgment based on the investigator's clinical experience, the association of the event with the study drug seems likely. The event disappears or decreases on cessation or reduction of the dose of study drug.
- Definite: This relationship suggests that a definite causal relationship exists between drug administration and the AE, and other conditions (concurrent illness, progression/expression of disease state, or reaction to concurrent medication) do not appear to explain the event. The event reappears or worsens if the study drug is re-administered.

6.4.5.9 Follow-Up of Subjects Reporting Adverse Events

All AEs must be reported in detail on the appropriate page in the eCRF and followed to satisfactory resolution, until the investigator deems the event to be chronic or not clinically significant, or until the subject is considered to be stable.

6.5 Pharmacokinetic and Pharmacodynamic Assessments

6.5.1 Pharmacokinetic Blood Samples

Serial blood samples (5 mL) for PK assessment of SKI-O-592 and its metabolites (M2 and M4) will be collected from all subjects in the PK/PD subset at the following time points:

- Day 1: 0 hour (morning pre-dose), and at 0.25 (+5 min), 0.5 (\pm 5min), 1, 2, 4, 8 and 12 hours (\pm 10 min) morning post-dose (12-hr sample should be collected prior to the evening dose).
- Week 12 (Day 84 or 85): 0 hour (morning pre-dose), and 0.25 (+5 min), 0.5 (\pm 5min), 1, 2, 4, 8, and 12 hours (\pm 10 min).

In addition, PK samples will also be collected at the following time points on Day 8 (\pm 2 days) from subjects in the safety run-in period only:

- Day 8 (\pm 2 days): 0 hour (morning pre-dose), and at 0.25 (+5 min), 0.5 (\pm 5min), 1, 2, 4, 8 and 12 hours (\pm 10 min) morning post-dose (12-hr sample should be collected prior to the evening dose).

For other subjects not included in the safety run-in period or PK/PD subset, morning pre-dose PK samples will be collected during Week 12 only.

When the PK blood sample collection coincides with safety assessments, PK blood samples should be collected as close to the scheduled time point as possible, and safety assessments should be performed before PK blood samples are taken.

For each sample collected, separated plasma will be transferred in approximately equal portions into 2 tubes that are labeled for sets A and B for SKI-O-592 and metabolites. Labels will include the study number, the subject identification number, an indication that they are PK samples, the nominal day and collection time, the analyte(s), and the set (A or B). Plasma samples will be stored at approximately -70°C in an upright position.

Set A samples will be transported, frozen with sufficient dry ice for several days, to the bioanalytical facility.

Set B samples will be retained at the study center until the study is completed and the clinical study report is issued, unless shipment to another facility is requested by the Oscotec Inc.

Instructions regarding the disposition of the B samples will be provided by the Oscotec Inc. Specific details and the full protocol for analysis of PK samples can be found in the study laboratory manual.

6.5.2 Pharmacokinetic Variables

Plasma PK parameters will be calculated for SKI-O-592 and its metabolites M2 and M4 in the PK/PD subset using a noncompartmental approach and will include the following, where applicable:

C_{max}	maximum observed concentration
T_{max}	time to reach the maximum observed concentration
$AUC_{0-\tau}$	area under the concentration versus time curve within a dosing interval
$t_{1/2}$	apparent terminal elimination half-life
K_{el}	terminal elimination rate constant
CL/F	apparent oral clearance (SKI-O-592 only)
V_z/F	apparent oral volume of distribution (SKI-O-592 only)
R_{met}	metabolite ratio
R_{AUC}	accumulation ratio based on $AUC_{0-\tau}$

Additional PK parameters may be estimated, as deemed appropriate.

6.5.3 Pharmacodynamic Blood Samples

Serial blood samples for assessment of the percentage of activated CD63+ basophils in peripheral blood will be collected in all subjects in the PK/PD subset at the following times:

- Day 1: 0 hour (morning pre-dose), and 0.25 (+5 min), 0.5 (± 5 min), 1, 2, 4, 8 and 12 hours (± 10 min) morning post-dose (12-hr sample should be collected prior to the evening dose).
- Day 84 or 85 (Week 12): 0 hour (morning pre-dose), and at 0.25 (+5 min), 0.5 (± 5 min), 1, 2, 4, 8, and 12 hours (± 10 min).

Blood samples must be dispatched to the processing laboratory as quickly as possible to ensure transport, cataloguing, and processing time is complete within the required timeframe

for the selected assay. All blood collection systems must be pyrogen free. Blood samples (0.5 mL) will be collected into tubes containing dipotassium ethylene diamine tetra acetic acid (K2 EDTA) anticoagulant. Tubes containing ethylene diamine tetra acetic acid or citric acid as anticoagulant are prohibited. Samples are to be stored at 2°C to 8°C prior to shipping and packed with ice pack for shipping.

Specific details and the full protocol for analysis of PD samples can be found in the study laboratory manual.

6.5.4 Pharmacodynamic Variables

The primary PD endpoint will be the change in the percentage of activated CD63+ basophils in peripheral blood. The PD parameters will include the following:

E_{max}	maximum effect
TE_{max}	time to achieve maximum effect
$AUEC_{0-\tau_{au}}$	area under the effect versus time curve within a dosing interval

Additional PD endpoints/parameters may be evaluated, as deemed appropriate.

6.6 Safety Monitoring Committee

An independent DMC appointed by the Sponsor will review the interim safety and PK data of the first 5 subjects enrolled in the safety run-in period. Further details will be provided in the DMC charter.

6.7 Pregnancy

Pregnancy is not regarded as an AE unless it is suspected that study drug interfered with the effectiveness of a contraceptive medication. Any pregnancy that occurs during study participation must be reported using a clinical study pregnancy form. To ensure subject safety, each pregnancy must be reported to the sponsor within 2 weeks of learning of its occurrence. The pregnancy must be followed up at least 30 days after birth or the first well-baby visit to determine the outcome (including spontaneous miscarriage, elective termination, normal birth, or congenital abnormality) and the status of mother and child, even if the subject was discontinued from the study. Pregnancy complications and elective

terminations for medical reasons must be reported as AEs or SAEs. Spontaneous miscarriages must be reported as SAEs.

Any SAE occurring in association with a pregnancy that is brought to the investigator's attention after the subject has completed the study and that is considered by the investigator as possibly related to the study drug must be promptly reported to the sponsor.

Contraception status will be monitored at each visit and documented appropriately.

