After dosing, all subjects will be subjected to safety assessments and a subset of at least 20 subjects, who are not included in the safety run-in period, will be subjected to PK and PD assessments according to the Schedule of Events ([Table 2](#)). Subjects enrolled in the safety run-in period will be admitted for 24 hours on Days 1, 8, and 84 or 85 of the study. Subjects selected for the PK/PD portion of the study will be admitted for 24 hours on Days 1 and 84 or 85 of the study.

The maximum duration of study participation for a subject will be 20 weeks, which consists of up to 4 weeks of screening period, 12 weeks of treatment period, and 4 weeks of follow-up period.

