4.1.1 Inclusion Criteria

Each subject must meet all of the following criteria to be enrolled in this study:

1. Able to provide written informed consent and agreeable to the schedule of assessments
2. Male or female subjects, aged 18 years or older (or ≥ 19 years of age for Korean subjects per local regulations)
3. Diagnosis of primary ITP (persistent or chronic) made according to the American Society of Hematology 2011 evidence-based guideline
4. Failed to respond or relapsed after at least 1 prior therapy (eg, corticosteroids, IVIG, anti-D, rituximab, TPO-receptor agonists, splenectomy, and immunosuppressants such as vincristine, mycophenolate mofetil, and azathioprine), with a platelet count of $<30,000/\mu\text{L}$ on 2 occasions at least 7 days apart with the confirmatory count being taken during Screening (the most recent result from the central laboratory will be considered as the confirmatory platelet count, when an unscheduled visit(s) is performed during the screening period). Response to such prior therapy is defined as platelet count of $\geq 30,000/\mu\text{L}$ and >2 times increase from baseline in the absence of bleeding. Failure to respond and relapse to such prior therapy are defined as failure to achieve and/or failure to maintain response on a tolerable regimen of prior therapy.
5. Adequate hematologic, hepatic, and renal function (absolute neutrophil count $\geq 1.5 \times 10^9/\text{L}$, hemoglobin [Hgb] $\geq 10.0 \text{ g/dL}$, aspartate aminotransferase [AST] and alanine aminotransferase [ALT] $\leq 2.0 \times \text{ULN}$, bilirubin $\leq 1.5 \times \text{ULN}$, albumin $\geq 3 \text{ g/dL}$, estimated glomerular filtration rate [eGFR] $\geq 40 \text{ mL/min/1.73m}^2$, and creatinine $\leq 1.5 \times \text{ULN}$)

6. ECOG performance status of 0, 1, or 2
7. Both male and female subjects must agree to take the following steps to reduce the potential for transmission of genetic material containing the investigational product:
 - a. Both male and female subjects, the subject and their partners of childbearing potential must agree to use 2 of the following medically acceptable methods of contraception from the time of randomization, during the study, and for 6 months following discontinuation of study drug, of which:
 - o One must be a highly reliable method of contraception, such as:
 - An intrauterine device or intrauterine system implanted for at least 30 days prior to Day 1

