 - Surgical sterilization of one of the partners for at least 6 months prior to the date of informed consent (assuming this will be the only partner for the whole duration of the clinical trial)
 - Consistent and correct use of hormonal contraceptives (hormonal implants, injectables, contraception pills, transdermal patches, or contraceptive rings) for at least 30 days prior to Day 1
 - o One supplementary barrier method, such as:
 - Male or female condom always with spermicide (a spermicidal foam/gel/film/cream)
 - Diaphragm or cervical/vault caps always with spermicide (a spermicidal foam/gel/film/cream)
 - Double-barrier methods (which means a barrier method used by both partners at the same time), even when used with spermicide, are not considered to be highly reliable contraception methods, and as such, may not be the only forms of contraception used
 - b. Female subjects must agree not to breastfeed starting from the time of Screening, throughout the study, and until after 6 months following the last dose of study drug.

- c. Male subjects must agree not to donate sperm starting from the time of randomization, throughout the study, and until after 6 months following the last dose of study drug
- d. For subjects and partners considered not of childbearing potential, the following conditions apply:
 - a. Menopausal females must have experienced their last period more than 12 months prior to the date of informed consent to be classified as not of childbearing potential.
 - b. Male and female subjects are in a situation of abstinence from heterosexual intercourse from Screening until after 6 months following the last dose of study drug when this is in line with the preferred lifestyle of the subject (eg, homosexual women and men or a member of a religious order such as nuns and priests).

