4.2 Withdrawal of Subjects From Study Drug and/or the Study

The duration of the study is defined for each subject as the date signed informed consent is provided through date of the last follow-up visit on Week 16.

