- * Subjects in the safety run-in period will have clinic visit on Week 2/Day 8 (± 2 days) for the mentioned assessments including hematology (differential) tests. For other subjects, this visit will be laboratory only visit to perform hematology (differential) tests only.
- a Clinic / laboratory visit windows are about ± 3 days for all dosing period and laboratory visits and about ± 1 week for clinic follow-up visits. The W12/D84 or D85 (EOT) visit should be performed while on therapy.
- b Complete physical examination at Screening and abbreviated physical examination at other visits.
- c For all subjects: predose ECG on the first day of dosing and on Day 1 of each subsequent week as specified in the table above. For subjects in the safety run-in subsets and PK/PD subset who are in safety run-in subset only: ECG on the first day of dosing at predose, 1, 2, 4, 8, and 12 hours (± 10 min) after the study drug administration.
- d For women of childbearing potential only: Serum pregnancy tests are performed at Screening. To confirm pregnancy, urine pregnancy test will be performed locally on Day 1 prior to randomization and prior to study drug administration on clinic visit days at mentioned timepoints. If urine pregnancy test is negative, dosing will be started; if urine pregnancy test is positive then with-hold dosing and perform a serum pregnancy test. FSH testing is needed at Screening for post-menopausal female subjects only.
- e Laboratory only visits will be performed on Day 4 ± 1 day (Week 1) for all subjects and on Week 2/Day 8 (± 2 days) for subjects other than those enrolled in the safety run-in period.
- f Study drug dispensing and administration can occur at unscheduled visit.
- g Samples to be collected as follows:

For the subjects in the safety run-in period only (for PK only; no PD assessments):

- Day 1: morning predose, 0.25 (± 5 min), 0.5 (± 5 min), 1, 2, 4, 8, and 12 hours (± 10 min) (evening predose).
- Day 8 (± 2 days): morning predose, 0.25 (± 5 min), 0.5 (± 5 min), 1, 2, 4, 8, and 12 hours (± 10 min) (evening predose).
- Week 12: morning predose, 0.25 (± 5 min), 0.5 (± 5 min), 1, 2, 4, 8, and 12 hours (± 10 min).

For the subjects in the PK/PD subset only (for PK/PD):

- Day 1: morning predose, 0.25 (± 5 min), 0.5 (± 5 min), 1, 2, 4, 8, and 12 hours (± 10 min) (evening predose).
- Week 12: morning predose, 0.25 (± 5 min), 0.5 (± 5 min), 1, 2, 4, 8, and 12 hours (± 10 min).

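### Pregnancy reporting ends at Week 16, about 4 weeks after a completer's last dose, while the protocol's contraception period runs to 6 months, leaving about 85% of the post-dose period without a duty to report a pregnancy as such

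*Protocol*

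**What the plan says.** **Reporting.** Protocol Section 6.7 sets the duty: "Any pregnancy that occurs during study participation must be reported using a clinical study pregnancy form". The sponsor must be told within 2 weeks of the site learning of a pregnancy. The pregnancy is then followed until at least 30 days after birth or the first well-baby visit, even if the subject has left the study. After study completion, the section asks only for an SAE associated with a pregnancy that comes to the investigator's notice and is considered possibly related. Section 6.4.5.3 has a similar causality condition for post-study SAEs in general.

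**End of participation.** Section 4.2 defines each subject's study duration as running from the "date signed informed consent is provided through date of the last follow-up visit on Week 16". Section 3.1 says "The maximum duration of study participation for a subject will be 20 weeks", including "12 weeks of treatment period, and 4 weeks of follow-up period".

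**Contraception period.** Section 4.1.1, criterion 7a, requires male and female subjects and their partners of childbearing potential to use two methods of contraception "from the time of randomization, during the study, and for 6 months following discontinuation of study drug". Breastfeeding is barred until 6 months after the last dose, and criterion 7c adds: "Male subjects must agree not to donate sperm starting from the time of randomization, throughout the study, and until after 6 months", counted from the last dose.

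**Early stoppers.** Section 1.4 says that subjects who discontinue treatment are followed for the intended duration of the study. Section 4.2.2 asks, whenever possible, for end-of-study assessments in those who stop drug permanently or withdraw.

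**Last checks.** In Table 2 the last scheduled pregnancy test and contraception check are at the Week 16 visit. The SAP plans no pregnancy summary.

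**The concern.** The protocol asks subjects and partners to avoid conception for 6 months after study drug, yet its own mechanism for learning about conceptions closes after about 4 of those 26 weeks in a completer. A pregnancy that begins in the remaining weeks and ends in a normal birth, or in an elective termination with no SAE, triggers no form. So does one with an adverse outcome that is judged unrelated or never volunteered. Those uneventful outcomes are the denominator against which any fetal signal would be read.

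Section 6.7 clearly intends to learn the outcome and the status of mother and child, and Section 1.1 describes clinical experience only in healthy subjects. Such pregnancies will be rare in a trial of about 60 subjects, but information on a missed one is hard to recover. Male subjects carry the 6-month restrictions too, and Section 6.7 leaves sites to guess whether a partner's pregnancy is reportable even during treatment.

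**Working it through.** The check is date arithmetic.

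**Inputs**
- Screening up to 4 weeks, treatment 12 weeks, follow-up 4 weeks (Protocol Section 3.1).
- Participation ends at Week 16 (Section 4.2).
- Contraception period: randomization to 6 months after study drug (Section 4.1.1, criterion 7). I take 6 months as 26 weeks, or 182.6 days. This conversion is an assumption; using 26.1 weeks moves no result by more than about 0.2 percentage points.
- Visit windows: ±3 days at the Week 12 visit (Table 2) and about ±1 "week for clinic follow-up visits" (Table 2, footnote a). The last dose is taken to fall at the Week 12 visit, which footnote a places on therapy.

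**Plan's own figure.** 4 + 12 + 4 = 20 weeks, matching the stated maximum.

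**Completer, nominal dates.** Covered: 4/26 = 15%. Uncovered: 26 − 4 = 22 weeks, and 22/26 = 85%.

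**Completer, follow-up window only.** With 3 to 5 weeks of follow-up, uncovered is 1 − 5/26 = 81% to 1 − 3/26 = 88%.

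**Completer, both windows.** Post-dose cover in days = (112 ± 7) − (84 ± 3).
- Shortest: 105 − 87 = 18 days; 1 − 18/182.6 = 90% uncovered.
- Longest: 119 − 81 = 38 days; 1 − 38/182.6 = 79% uncovered.

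**Completer, whole period from randomization.** 12 + 26 = 38 weeks, of which 16 are covered. Uncovered: 22/38 = 58%.

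**Early stopper followed to Week 16.** For a stop after *s* weeks, cover is 16 − *s* weeks and the uncovered share is 1 − (16 − *s*)/26.

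| Stop | Post-dose weeks covered | Weeks uncovered | Share uncovered |
|---|---|---|---|
| Day 1 | 16 | 10 | 38% |
| Week 3 | 13 | 13 | 50% |
| Week 6 | 10 | 16 | 62% |
| Week 9 | 7 | 19 | 73% |
| Week 12 | 4 | 22 | 85% |

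The gap never falls below about 10 weeks. It reaches 100% only if participation itself ends when drug is stopped, for example when a subject withdraws and has the end-of-study assessments then (Section 4.2.2).

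**Does any other passage fill the gap?** The post-study clauses in Sections 6.7 and 6.4.5.3 apply to possibly related SAEs, not to a pregnancy as such. The instruction in Section 6.4.5.1 to contact the investigator concerns symptoms. The 2-week deadline in Section 6.7 follows the participation sentence; it sets the timing of a report and does not extend the window. No visit follows Week 16.

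**The case against.** The strongest reply is that a contraception undertaking by the subject and a reporting duty on the site are different things, and a precautionary contraception period may reasonably outlast active reporting. The criterion does not say that fetal exposure persists for 6 months, and the text of Section 1.2 is missing from the public copy, so the basis for the period cannot be seen. That stands: this is a mismatch between two periods, not a demonstrated 6-month fetal hazard. It does not explain why an outcome that Section 6.7 wants to know should go uncollected for most of the period in which the protocol asks people not to conceive.

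Four stronger readings are tempting, and the documents do not support them.
- *All reporting stops at Week 16.* It does not. A congenital anomaly is an SAE (Section 6.4.5.2), a spontaneous miscarriage must be reported as one (Section 6.7), and possibly related SAEs stay reportable after the study. The route is passive and depends on a causality judgement, so outcomes may be missed, not will be.
- *Stopping drug early leaves the whole period uncovered.* Section 1.4 keeps such subjects in follow-up, which gives them more post-dose cover than a completer.
- *Partner pregnancies are excluded.* Section 6.7 refers to any pregnancy. It is silent on partners, so this part is a request for clarification.
- *85% of pregnancies would be lost.* The figure is a share of calendar time after dosing, not of events.

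The consent pages and the pregnancy form were not available. Either could already ask subjects to notify the site after the last visit.

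**Conclusion.** The mismatch is real and worth correcting. For a completer, about 22 of about 26 post-dose weeks (85%; roughly 79% to 90% with visit windows) fall inside the contraception period but outside the duty to report a pregnancy and follow its outcome. The share is lower for early stoppers who remain in follow-up. Passive reporting of possibly related SAEs narrows the consequence but does not close the gap. Whether partner pregnancies are covered is unclear.

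The conclusion rests on three assumptions: 6 months is about 26 weeks, a completer's last dose is at about Week 12, and participation ends as Section 4.2 defines it. No endpoint or planned efficacy analysis is affected; the point concerns completeness of safety data.

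**What to change.** In Protocol Section 6.7:
- Keep the present start of reporting (study participation, from signed consent). Starting at first dose would drop pregnancies between consent and dosing, and would not match criterion 7a, which begins at randomization.
- Move the end of pregnancy reporting to 6 months after the last dose, in line with criterion 7. For a completer this takes post-dose cover from about 4 to about 26 weeks, and cover from randomization from about 16 to about 38 weeks. Even after a Day 1 stop, 26 weeks runs past Week 16, so no dosed subject loses present cover.
- State that the duty covers female subjects and partners of male subjects, with the partner's consent.
- Have sites instruct subjects at their last visit to notify them of any pregnancy in that period.

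The existing form, 2-week deadline and outcome follow-up can stay, as can the contraception rule itself. Check the consent form for consistency and amend it if needed. No visits or tests are added. The cost is a wording change and small site effort for rare reports and partner consent.
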